3.11.3 Blanking Period

The Blanking Period consists of Day 0 (the date of Index Procedure) through and including Day 90.

During the Blanking Period, any recurrence of AF will be documented; however, recurrences of AF, AFL or AT during this time will not be considered Therapeutic Failures.

Subjects may undergo one repeat ablation during the Blanking Period without creating a Therapeutic Failure, following the procedure detailed in the preceding sections. This may occur during the Remap Procedure or at another procedure as clinically indicated.

If a second repeat ablation procedure is performed during this time, or any nonstudy device is used for cardiac ablation, the subjects will be considered a Therapeutic Failure but will remain in the study.

Towards the end of the Blanking Period, any AFD treatment will be discontinued unless the Investigator deems the withdrawal of AFD treatment not to be in the best interests of the patient.

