6.4 Secondary Feasibility Endpoints

1. The proportion of subjects who undergo the protocol-specified 75-Day Remapping Procedure and achieve Chronic Procedural Success (CPS) defined as persistent electrical isolation of all initially ablated pulmonary veins. Chronic Procedural Success will be subdivided by Index Procedure only CPS and Reablated CPS subjects.

2. The proportion of attempted subjects that achieve Acute CTI Success, defined as the creation of bi-directional electrical block across the CTI using the investigational devices.
3. Durability of the CTI and/or other extra-PV lesion set(s), when applicable. Durability is defined as unaltered integrity of each such lesion assessed at the Remapping Procedure.
4. The proportion of subjects that achieve Therapeutic Success, defined as freedom from:
 - a. Post-Blanking Period through assessment: occurrence of AF, AFL or AT, or ablation for AF/AFL/AT using the study device
 - b. At any time: ablation for AF/AFL/AT with a nonstudy deviceTherapeutic Success will be assessed from the end of the 90 Day Blanking Period through Months 6 and 12 and will be subdivided by on / off AFDs (Atrial Fibrillation Drugs) post-Blanking Period.

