2.1.3. Descriptive Statistics in Summary Tables

- *Continuous variables* will be summarized using standard quantitative statistics: number of non-missing observations, mean, standard deviation, median, quartiles and range (minimum and maximum observed values). The number of missing observations will also be specified.
- *Categorical variables* will be summarized using classical frequency statistics: number of non-missing observations and percentages by categories. Percentages will be calculated on the number of non-missing observations and will be displayed using one decimal. The number of missing observations will also be specified.

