2.4.6.2. Secondary Feasibility Analysis

The secondary feasibility analyses are:

- The proportion of subjects who undergo the protocol-specified 75-Day Remapping Procedure and achieve Chronic Procedural Success (CPS) defined as persistent electrical isolation of all initially ablated pulmonary veins. Chronic Procedural Success will be subdivided by Index Procedure only CPS and Reablated CPS subjects.
- The proportion of attempted subjects that achieve Acute CTI Success, defined as the creation of bi-directional electrical block across the CTI using the investigational devices.
- Durability of the CTI and/or other extra-PV lesion set(s), when applicable.
Durability is defined as unaltered integrity of each such lesion assessed at the Remapping Procedure.
- The proportion of subjects that achieve Therapeutic Success, defined as freedom from:
 - Post-Blanking Period through assessment: occurrence of AF, AFL or AT, or ablation for AF/AFL/AT using the study device
 - At any time: ablation for AF/AFL/AT with a non-study device
Therapeutic Success will be assessed from the end of the 90 Day Blanking Period through Months 6 and 12 and will be subdivided by on / off AADs (Atrial Fibrillation Drugs) post-Blanking Period.

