Toute reproduction ou distribution, totale ou partielle, de ce document, sans autorisation préalable de ICON PLC est interdite.
Reproduction and distribution of this document, in whole or in part, is strictly forbidden without prior authorization from ICON PLC.

	STATISTICAL ANALYSIS PLAN	FARAPULSE PersAFOne SAP V1.0 PERSAFONE Page 24 /49
---	----------------------------------	--

ELSE IF Ablation with study device was successful = 'No' in **procedural form (PR)** **THEN**
APS='No'

Secondary Feasibility Analysis

- Derived criteria "Chronic Procedural Success (CPS)" will be defined as follows:
IF Has all ablation with the study device(s) been successful? ='Yes' in **Procedural data form (PR)** **AND** Has all ablation with the study device remain successful? ='Yes' **AND** Additional ablation(s) performed? ='No' in **FOLLOW UP 3D ELECTRO ANATOMICAL MAPPING form (RM)** **THEN** Chronic Procedural Success (CPS) ='Yes, index procedure only'
ELSE IF Has all ablation with the study device(s) been successful? ='Yes' in **Procedural data form (PR)** **AND** Has all ablation with the study device remain successful? ='No' **AND** Any PV reconnections noted? in = 'Yes' **AND** Additional ablation(s) performed? ='Yes' in **FOLLOW UP 3D ELECTRO ANATOMICAL MAPPING form (RM)** **THEN** Chronic Procedural Success (CPS) ='Yes, reblated'
ELSE IF Has all ablation with the study device(s) been successful? ='No' in **Procedural data form (PR)** **THEN** Chronic Procedural Success (CPS) ='No'
- Derived criteria Proportion "Acute Cavotricuspid isthmus (CTI) Success" will be defined as follows:
COUNT IF [CTI isolated/Blocked='Yes' AND CTI Attempted='Yes'] in **Procedural data form (PR)**
- Derived criteria "Durability of CTI at remap," will be defined as follows:
IF CTI lesion durable ='Yes' in **Follow-up 3D electroanatomical mapping form (RM)** **THEN** Durability of CTI at remap = 'Yes'
ELSE IF CTI lesion durable ='No' in **Follow-up 3D electroanatomical mapping form (RM)** **THEN** Durability of CTI at remap = 'No'
- Derived criteria "Durability of Mitral isthmus at remap" will be defined as follows:
IF Mitral isthmus lesion durable ='Yes' in **Follow-up 3D electroanatomical mapping form (RM)** **THEN** Durability of Mitral isthmus at remap = 'Yes'
ELSE IF Mitral isthmus lesion durable ='No' in **Follow-up 3D electroanatomical mapping form (RM)** **THEN** Durability of Mitral isthmus at remap = 'No'

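### The SAP's Chronic Procedural Success rule cannot return 'No' for a vein found reconnected at remap, and its 'Durable PVI' line also requires five non-PV lesions to be durable

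*SAP*

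**What the plan says.** Protocol 6.4 lists as its first secondary feasibility endpoint "Chronic Procedural Success (CPS) defined as persistent electrical isolation of all initially ablated pulmonary veins", among subjects who are remapped. SAP 2.4.6.2 repeats the definition and adds "Chronic Procedural Success will be subdivided by Index Procedure only CPS and Reablated CPS subjects".

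SAP 2.5 turns this into three branches with no final ELSE:

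1. Index item 'Yes', remap item on continued success 'Yes', and "Additional ablation(s) performed? ='No' in" the remap form: 'Yes, index procedure only'.
2. Index item 'Yes', continued success 'No', "Any PV reconnections noted? in = 'Yes", and additional ablation 'Yes' on the remap form: "Chronic Procedural Success (CPS) ='Yes, reblated".
3. "Has all ablation with the study device(s) been successful? ='No' in" the procedural (index) form: 'No'.

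SAP 2.1.2 rules out replacing missing values. SAP 2.1.3 adds: "Percentages will be calculated on the number of non-missing observations and will be displayed using one decimal". SAP Table 13 has a single CPS row.

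On re-ablation in the blanking period, Protocol 3.11.3 says: "This may occur during the Remap Procedure or at another procedure as clinically indicated".

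Separately, SAP 2.5 defines 'Durable PVI', a descriptive line in Table 5, as 'Yes' only if eleven lesion fields on the remap form are all 'Yes', and otherwise 'No'.

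**The concern.** The remap exists to test durability, yet the SAP's CPS rule uses the reconnection finding only as a condition for a 'Yes'. A durability endpoint that no remap finding can fail does not measure durability. It looks like an oversight: the derivations that follow in SAP 2.5 (CTI, mitral isthmus, roof line, posterior line) each assign 'No' when the remap form says the lesion is not durable.

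The study is descriptive and is meant to inform later studies (Protocol 5.3), so the printed rate is the result. The other subject-level PV line, 'Durable PVI', fails in the opposite direction. The same patients could therefore show CPS near 100% and 'Durable PVI' near 0%.

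**Working it through.** The documents give no CPS rate to reproduce. The check has three parts.

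**1. Enumerating the rule.** The inputs are the four Yes/No items in SAP 2.5: index success, continued success, PV reconnection, additional ablation. With index 'No', all 8 combinations of the other three give 'No'. With index 'Yes', the 8 combinations give 2 'Yes, index only', 1 'Yes, reablated', 5 no value and 0 'No'. So for every subject given a value, 'Yes' is identical to index success.

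The clinical patterns after index success are below. They assume the all-ablation items are completed as worded: continued success means no PV and no extra-PV loss.

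| PVs at remap | Extra-PV loss | Ablation added at remap | CPS |
|---|---|---|---|
| durable | no | no | Yes, index only |
| durable | no | yes | no value |
| durable | yes | no | no value |
| durable | yes | yes | no value |
| reconnected | no | yes | Yes, reablated |
| reconnected | yes | yes | Yes, reablated |
| reconnected | no | no | no value |
| reconnected | yes | no | no value |

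Again there are 3 'Yes', 5 no value and 0 'No'. These count patterns, not how often they occur. The reablated 'Yes' checks neither which structure was ablated nor whether the vein was re-isolated.

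**2. Effect on the printed row.** Inputs: 39 of 49 remapped patients with all PVs isolated (Protocol 1.3.2) and 14 of 35 (Protocol 1.3.1). Assumptions: index success in everyone and every PV-durable patient classified. The number of reconnected patients re-ablated is not given, so the range from none to all is shown.

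- All-PV durability: 39/49 = 79.6% (exact 95% CI 65.7–89.8) and 14/35 = 40.0% (23.9–57.9).
- Reconnected: 49 − 39 = 10 and 35 − 14 = 21.
- With r re-ablated and d durable, the denominator is d + r. A pooled row is (d + r)/(d + r); an index-only row is d/(d + r).

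| Re-ablated | Pooled, d = 39 | Index-only, d = 39 | Pooled, d = 14 | Index-only, d = 14 |
|---|---|---|---|---|
| none | 39/39 = 100% | 39/39 = 100% | 14/14 = 100% | 14/14 = 100% |
| 5 of 10; 10 of 21 | 44/44 = 100% | 39/44 = 88.6% | 24/24 = 100% | 14/24 = 58.3% |
| all | 49/49 = 100% | 39/49 = 79.6% | 35/35 = 100% | 14/35 = 40.0% |

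With none re-ablated, 10/49 = 20.4% and 21/35 = 60.0% of patients have no value.

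At 100%, SAP 2.1.4 allows the Agresti-Coull interval. For 39/39 the centre is (39 + 1.92)/(39 + 3.84) = 0.955, and the lower limit is 0.955 − 1.96·√(0.955·0.045/42.84) = 89.3%. For 14/14 it is 74.9%. Pooled with all re-ablated, the limits are 91.3% (49/49) and 88.2% (35/35).

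**3. 'Durable PVI'.** There are six PV fields: left superior, left inferior, left common ostium, right middle, right superior and right inferior. There are five others: CTI, mitral isthmus, roof line, posterior line and Other 1. Total 6 + 5 = 11. Separate left veins and a left common ostium would not normally be recorded together, and extra-PV lesions are at the investigator's discretion (Protocol 3.2). Unless lesions that were never made are coded as durable, almost every subject falls to the ELSE ('No'). Under the general rule opening SAP 2.5, a missing component instead makes the line missing.

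**The case against.** Four points on the other side have weight.

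- **Pooling.** A reader might infer that the CPS row simply reports index success. That needs Table 13 to pool both 'Yes' levels. The table does not say so, its asterisk has no footnote in the available text, and SAP 2.1.3 calls for percentages by category. If the row counts index-only CPS and every reconnected subject is re-ablated, it prints the correct 79.6% and 40.0%. This stands. Untreated reconnections are still lost under either reading.
- **The reablated category.** A reader might infer that counting re-ablated subjects as successes is the SAP's error. The documents do not support that. The protocol makes reablated subjects a subdivision of CPS without saying when the re-ablation occurs. The SAP takes additional ablation from the remap form and so places it at the remap. Counting those subjects may follow the protocol.
- **Form meaning.** The CRF is not available. SAP 2.5 derives Acute Procedural Success, a PV-only endpoint, from a similarly general item, so sites may complete the all-ablation items for PVs only. The loss of PV-durable subjects with an extra-PV lesion failure is therefore conditional. The absence of a remap 'No' is not.
- **Other outputs.** A reader might infer that durability is hidden. It is not: Tables 5, 6 and 11 give per-vein results, Listing 13 is by subject, and SAP 2.1.3 requires the missing count. The subject-level rate is what fails.

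The no-re-ablation case is also an extreme, since Protocol 3.12.5 lets investigators close gaps at remap. The same discretion makes an untreated reconnection foreseeable.

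**Conclusion.** The concern holds on the text of SAP 2.5. After index success, no remap finding yields CPS 'No' (0 of 8 patterns on either enumeration, 5 of 8 unclassified). The SAP's own faults are the missing 'No', the missing check on structure and re-isolation, the subjects dropped from the denominator, and a Table 13 row without the promised split.

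The size depends on Table 13 and on how many reconnected subjects are re-ablated. In the illustrations, a pooled row prints 100% throughout. An index-only row runs from 100% (none re-ablated) to the correct 79.6% or 40.0% (all re-ablated). With none re-ablated the reablated category is empty, so the whole gap comes from the missing 'No'. With all re-ablated, the gap in a pooled row may be the protocol's own definition. The counts come from earlier studies in paroxysmal AF patients (Protocol 4.3), under the assumptions stated above. They are not predictions for this trial.

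'Durable PVI' is a separate, smaller fault in a descriptive line. As written it is near 0% or not estimable, whatever the true PV durability. Both should be corrected before the analysis is run.

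**What to change.** Among all remapped subjects, derive index-only CPS from the per-vein fields, in this order:

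1. 'No' if any PV ablated at index was not isolated at index, or is reconnected at remap as assessed before any remap ablation.
2. Otherwise 'Unclassified' if any treated vein's field is missing.
3. Otherwise 'Yes'.

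Ignore non-PV lesions and extra-PV ablation. Flag subjects known to have had a PV re-ablated between index and remap, if the CRF records it, and report them separately.

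Print index-only CPS and Reablated CPS on separate Table 13 rows, with the number unclassified. The sponsor should state, for Reablated CPS, when the re-ablation occurs and how re-isolation is shown. If it occurs at the remap, say that this row overlaps the index-only 'No' group.

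Define 'Durable PVI' as durability of all PVs treated at index in that subject, ignoring absent veins and all non-PV lesions.

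The cost is SAP wording, programming and a table row. SAP 2.5 already names the per-vein index and remap fields. Two items need checking against the CRF: whether ablations between visits record the structure treated, and whether the remap form records isolation after remap ablation. The CPS figure may come out less favourable.

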PLANNED PROCEDURE:	
Index Procedure:
 
Subjects will undergo an attempt to isolate all pulmonary veins or their anatomic equivalent.Subjects with a past history of atrial flutter, who are at risk of atrial flutter, who present with atrial flutter during the Index Procedure or who have inducible cavotricuspid isthmus-mediated (typical) flutter may undergo ablation of the cavo-tricuspid isthmus at the discretion of the investigator.Additional left atrial lesions may be made at the discretion of the investigator including focal sites, electrical gaps and lines of isolation. 
75-Day Remap Procedure:
 
Subjects will undergo a remapping procedure at 75 ± 15 days to assess the durability of the ablation lesions performed during the Index Procedure.During this procedure, additional ablations may be made at the discretion of the investigator to optimize patient outcomes.

PRIMARY SAFETY ENDPOINT:	
The primary safety endpoint for this study is the Composite Safety Endpoint (CSE) defined as the incidence of the following early-onset and late-onset serious adverse events (SAEs) which are device- or procedure-related, as adjudicated by the CEDMC. (See Table 4. Composite Safety Endpoint Definitions in Section 6.1).
 
Early onset (within 30 days of an Index or Remap Procedure)
 
• Death• Myocardial infarction (MI)• Persistent diaphragmatic paralysis• Stroke or transient ischemic attack (TIA)• Peripheral or organ thromboembolism• Pericarditis• Cardiac tamponade / perforation• Vascular access complications requiring intervention• Heart block 
Late onset (any time during follow-up through 12 months)
 
• Pulmonary vein (PV) stenosis (> 70% diameter reduction from baseline)• Atrio-esophageal fistula
SECONDARY SAFETY ENDPOINTS:	
1. The Primary Safety Endpoint assessed at 7 days2. The proportion of subjects with a device- or procedure-related SAE3. The proportion of subjects with stroke or TIA4. The proportion of subjects requiring cardioversion5. The proportion of subjects requiring an arrhythmia-related (AF, AFL or AT) hospitalization

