Reproduction and distribution of this document, in whole or in part, is strictly forbidden without prior authorization from ICON PLC.

	STATISTICAL ANALYSIS PLAN	FARAPULSE PersAFOne SAP V1.0 PERSAFONE Page 20 /49
---	----------------------------------	--

ELSE IF Pacemaker, Implantable Cardioverter Defibrillator or Cardiac Resynchronization therapy device ='No' in **Patient eligibility Form (IE)** **THEN** Permanent pacemaker or ICD='No'

Index Procedure:

- Derived criteria "Procedure time (hours)" will be defined as follows:
Procedure end- Procedure start in **Procedural data form (PR)**.
- Derived criteria "FARAWAVE dwell time (hours)" will be defined as follows:
SUM of [(FARAWAVE ablation catheter remove 1 – FARAWAVE ablation catheter introduction 1), (FARAWAVE ablation catheter remove n – FARAWAVE ablation catheter introduction n)] in **Procedural data form (PR)**
- Derived criteria "PVI ablation time (hours)" will be defined as follows:
Last PVI ablation time - First PVI ablation time in **Procedural data form (AB)**
- Derived criteria "CTI (FARAFLEX) dwell time (hours)" will be defined as follows:
SUM of [(FARAFLEX ablation catheter remove 1 – FARAFLEX ablation catheter introduction 1), (FARAFLEX ablation catheter remove n – FARAFLEX ablation catheter introduction n)] in **Procedural data form (PR)**
- Derived criteria "LAPW ablation time (hours)" will be defined as follows:
Last LAPW ablation time - First LAPW ablation time in **Procedural data form (AB)**
- Derived criteria "Total number of PVI applications" will be defined as follows:
SUM of [(Count (Ablation location **IN** ("Left superior", "Left inferior", "Right superior", "Right inferior", "Right middle", "Left common ostium") **OR** (Ablation location='Other' **AND** Ablation location, Other specify='LCPV')))] in **Procedural data form (AB)**
- Derived criteria "Number of LAPW applications" will be defined as follows:
SUM of [(Count (Ablation location='Other' **AND** Ablation location, Other specify **IN** ("LA PW", "LAPW", "LEFT ATRIAL POSTERIOR WALL")))] in **Procedural data form (AB)**
- Derived criteria "Total number of CTI applications" will be defined as follows:
SUM of [(Count (Ablation location=" CTI"))] in **Procedural data form (AB)**
- Derived criteria "Total number of veins treated" will be defined as follows:

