IF Anatomical Structure/Area other specification 1 **IN** ("POSTERIOR WALL" "LA POSTERIOR WALL" "LAPW" "PA WALL" "BOX POSTERIOR WALL") **AND** Other 1 Lesion durable = 'yes' **OR** Anatomical Structure/Area other specification 2 **IN** ("POSTERIOR WALL" "LA POSTERIOR WALL" "LAPW" "PA WALL" "BOX POSTERIOR WALL") **AND** Other 2 Lesion durable = 'Yes' in **Follow-up 3D electroanatomical mapping form (RM)** **THEN** LAPW chronic isolation= 'Yes'
ELSE LAPW chronic isolation = 'No'
- Derived criteria "Number of veins durably isolated" will be defined as follows:
SUM of [LSPV chronic isolation='Yes', LIPV chronic isolation='Yes', LCPV chronic isolation='Yes', RSPV chronic isolation='Yes', RIPV chronic isolation='Yes', RMPV chronic isolation ='Yes'] in **Follow-up 3D electroanatomical mapping form (RM)**
- Derived criteria "Number of veins with gaps" will be defined as follows:
SUM of [LSPV chronic isolation='No', LIPV chronic isolation=' No', LCPV chronic isolation=' No', RSPV chronic isolation=' No', RIPV chronic isolation=' No', RMPV Chronic isolation = 'No'] in **Follow-up 3D electroanatomical mapping form (RM)**

6 and 12 Months follow up

- Derived criteria "TTM compliance (%) (calculated)" will be defined as follows:
(TTM weeks received /TTM weeks expected) *100 in **MDT excel file**
- Derived criteria "Holter compliance (%) at 6 months" will be defined as follows:

CONFIDENTIEL / CONFIDENTIAL

Toute reproduction ou distribution, totale ou partielle, de ce document, sans autorisation préalable de ICON PLC est interdite.
Reproduction and distribution of this document, in whole or in part, is strictly forbidden without prior authorization from ICON PLC.

	STATISTICAL ANALYSIS PLAN	FARAPULSE PersAFOne SAP V1.0 PERSAFONE Page 22 /49
---	----------------------------------	--

IF 6mo Holter in ('AF', 'none', 'SVT') in **MDT excel file** **THEN** Holter compliance (%) at 6 months = 'Yes'

ELSE IF 6mo Holter in ('MISSING') in **MDT excel file** **THEN** Holter compliance (%) at 6 months='No'

- Derived criteria "Holter compliance (%) at 12 months" will be defined as follows:

IF 12mo Holter in ('AF', 'none', 'SVT') in **MDT excel file** **THEN** Holter compliance (%) at 12 months = 'Yes'

ELSE IF 12mo Holter in ('MISSING') in **MDT excel file** **THEN** Holter compliance (%) at 12 months='No'

- Derived criteria "Freedom from AF/AFL/AT" will be defined as follows:

IF AF/AFL/AT status =0 in **MDT excel file** **THEN** Freedom from AF/AFL/AT ='Yes'

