- Derived criteria "Durability of Left atrial roof line at remap" will be defined as follows:
IF Left atrial roof line lesion durable ='Yes' in **Follow-up 3D electroanatomical mapping form (RM)** **THEN** Durability of Left atrial roof line at remap = 'Yes'
ELSE IF Left atrial roof line lesion durable ='No' in **Follow-up 3D electroanatomical mapping form (RM)** **THEN** Durability of Left atrial roof line at remap = 'No'
- Derived criteria "Durability of Left atrial Posterior line" will be defined as follows:
IF Left atrial Posterior line lesion durable ='Yes' in **Follow-up 3D electroanatomical mapping form (RM)** **THEN** Durability of Left atrial Posterior line at remap = 'Yes'
ELSE IF Left atrial Posterior line lesion durable ='No' in **Follow-up 3D electroanatomical mapping form (RM)** **THEN** Durability of Left atrial Posterior line at remap = 'No'
- Derived criteria "Therapeutic Success ON/OFF AAD" will be defined as follows:

CONFIDENTIEL / CONFIDENTIAL

Toute reproduction ou distribution, totale ou partielle, de ce document, sans autorisation préalable de ICON PLC est interdite.
Reproduction and distribution of this document, in whole or in part, is strictly forbidden without prior authorization from ICON PLC.

IF "AF/AFL/AT status"= 0 **AND** "RF touchup"= 0 **AND** "ABL >90 days" = 0 **in MDT excel file**
THEN therapeutic success='Yes'
ELSE therapeutic success='No'

- Derived criteria "Therapeutic Success Off ADD" will be defined as follows:
IF Therapeutic success ='Yes' **AND** Class I/III AAD>90days=0 **in MDT excel file** **THEN** therapeutic success Off ADD ='YES'
ELSE IF Therapeutic success ='No' **AND** Class I/III AAD>90days=0 **in MDT excel file** **THEN** **THEN** therapeutic success Off ADD ='NO'
- Derived criteria "Therapeutic Success On ADD" will be defined as follows:
IF Therapeutic success ='Yes' **AND** Class I/III AAD>90days=1 **in MDT excel file** **THEN** therapeutic success On ADD ='No'
Else If Therapeutic success ='No' **AND** Class I/III AAD>90days=1 **in MDT excel file** **THEN** **THEN** therapeutic success On ADD ='No'

Additional endpoints

- Derived criteria "Proportion of all ablated pulmonary veins that are isolated at the Index Procedure using the study device" will be defined as follows:

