4.1.13. Table 13. Secondary Feasibility Endpoints

	ITT Population	
	N = XX	[95% CI]
Chronic Procedural Success (CPS)* for subjects who undergo the protocol-specified 75-Day Remapping Procedure	XX/XX (XX.X%)	[XX% - XX%]
Acute Cavotricuspid isthmus (CTI) Success**	XX/XX (XX.X%)	[XX% - XX%]
Therapeutic Success***	XX/XX (XX.X%)	[XX% - XX%]
On AADs	XX/XX (XX.X%)	[XX% - XX%]
Off AADs	XX/XX (XX.X%)	[XX% - XX%]
Durability of the CTI and/or other extra PV lesion set(s)	XX/XX (XX.X%)	[XX% - XX%]

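### The Table 13 durability row omits the 'Other' remap fields that hold posterior-wall lesions, and nothing says how its single figure is formed

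*SAP*

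**What the plan says.** **Endpoint.** Protocol 6.4 and SAP 2.4.6.2 list as a secondary feasibility endpoint "Durability of the CTI and/or other extra-PV lesion set(s), when applicable". SAP 2.4.6.2 adds: "Durability is defined as unaltered integrity of each such lesion assessed at the Remapping Procedure".

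**Which lesions can occur.** The set is open-ended. The planned procedure in the Protocol's Executive Summary states: "Additional left atrial lesions may be made at the discretion of the investigator including focal sites, electrical gaps and lines of isolation".

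**Derivation.** Under Secondary Feasibility Analysis, SAP 2.5 defines four yes/no durability variables. They begin with "Durability of CTI at remap", continue with mitral isthmus and left atrial roof line, and end with "Durability of Left atrial Posterior line". The next item is Therapeutic Success.

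**Where the posterior wall is recorded.** In the Index Procedure part of SAP 2.5, "Number of LAPW applications" counts entries whose location is 'Other' and whose free text names the posterior wall. In the part on remapping at 75 days, LAPW chronic isolation is read from the 'Other 1' and 'Other 2' specifications together with their durability fields (for example "Other 2 Lesion durable"). The same rule is repeated under Additional endpoints.

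**Tables.** Table 13 has one row for the durability of the CTI and other extra-PV lesion sets. Table 5 has separate rows for CTI and for LAPW chronic isolation, each with a 95% confidence interval. Table 11 has a Chronic CTI Success row and a Chronic Focal Success row.

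**The concern.** The posterior wall is the left-atrial extra-PV lesion that the SAP follows most closely: it has its own ablation time, application count and remap row. Yet it is missing from the secondary endpoint that is meant to cover extra-PV durability. If few mitral, roof or posterior lines are made, the Table 13 figure is largely CTI durability under a label that promises more.

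The single row adds a second problem. Four separate variables have to become one n/N, and the SAP does not say how. A count of lesions, a count of subjects with every lesion durable, and a count of subjects with any lesion durable all fit the text. Results are meant to inform later studies, so a reader who takes the Table 13 figure as the extra-PV durability estimate could be misled about what it covers.

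**Working it through.** The plan gives no figure to reproduce. The check sets each remap lesion field against its derivation and its table row.

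| Lesion (remap field) | In the secondary durability derivation? | Own table row? |
|---|---|---|
| CTI | yes | yes, Tables 5 and 11 |
| Mitral isthmus | yes | no |
| Left atrial roof line | yes | no |
| Left atrial posterior line | yes | no |
| Posterior wall ('Other 1/2') | no | yes, Table 5 |
| Other lesions entered in 'Other 1/2' | no | no |

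**Is the posterior line the same field as the posterior wall?** The Durable PVI rule in SAP 2.5 lists the left atrial posterior line and 'Other 1' as separate remap fields, and the LAPW rule reads only the 'Other' fields. As coded, the posterior-line variable does not pick up LAPW.

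**Does Table 11 fill the gap?** Its Chronic Focal Success row is labelled as covering all targeted extra-PV tissue except the CTI. SAP 2.5 has no variable of that name. The only candidate under Additional endpoints is LAPW chronic isolation, which leaves out the mitral, roof and posterior lines.

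**Combining rule.** Take one assumed subject with a durable CTI line and a non-durable roof line. Counted by lesion the result is 1/2, by subject with all lesions durable 0/1, and by subject with any lesion durable 1/1. The SAP does not choose.

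**Size, with assumed counts.** Suppose 12 CTI lines, all durable, 24 posterior walls, 18 durable, and no other extra-PV lesions.

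- As derived: 12/12 = 100%. SAP 2.1.4 uses the Agresti-Coull interval at 100% when the asymptotic assumptions fail. With z² = 3.84, ñ = 12 + 3.84 = 15.84 and p̃ = (12 + 1.92)/15.84 = 0.879. The lower limit is 0.879 − 1.96 × √(0.879 × 0.121/15.84) = 71.8%.
- With the posterior wall included, counted by lesion: (12 + 18)/(12 + 24) = 30/36 = 83.3%. The asymptotic interval is 0.833 ± 1.96 × √(0.833 × 0.167/36) = 71.2% to 95.5%. If its assumptions are not accepted, the exact interval is 67.2% to 93.6%.
- By lesion: CTI 100%, posterior wall 18/24 = 75.0% (exact 53.3% to 90.2%).

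**Denominator of the LAPW row.** The four secondary rules assign 'No' only when the field says no. The LAPW rule ends in an unconditional ELSE 'No'. Read literally, a remapped subject who never had a posterior-wall lesion counts as not durable. With 6 such subjects (assumed), 18/24 = 75.0% would become 18/30 = 60.0%. The missing-item rule at the head of SAP 2.5 might override this, but the SAP does not say so.

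**The case against.** The strongest reply is that the two lesions at the centre of the argument are already reported separately. Table 5 gives CTI and LAPW durability with confidence intervals in the ITT population, from the same remap form. The study is descriptive with no hypothesis test, so no decision turns on which table carries a number, and a poorly durable posterior wall would be visible. This stands, and it is why the point is minor.

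Three stronger readings are tempting, and the documents do not support them:

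- A reader might infer that durability lesion by lesion is absent from the planned output. That is wrong for CTI and the posterior wall. It is right only for mitral isthmus, roof line, posterior line and the remaining 'Other' lesions.
- A reader might infer that the SAP prescribes a pooled proportion. It defines four separate variables and one table row; pooling is a guess at how they meet. The supported criticism is that the row is undefined.
- A reader might infer that every posterior-wall lesion is lost to the endpoint. The case report form is not among the documents, and some sites may have used the structured posterior-line field.

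The reply does not remove the gap in the endpoint itself. Table 5 describes the remap and does not redefine the secondary endpoint, its LAPW rule has the denominator problem shown above, and three derived variables still have no visible result of their own.

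**Conclusion.** The concern holds as a minor error in the derivation and table shell. Followed as written, the Table 13 durability endpoint omits lesions recorded under 'Other', which is where the SAP's code places the posterior wall, and its single row has no stated numerator, denominator or combining rule. Four lesion categories have no row anywhere: mitral isthmus, roof line, posterior line and non-posterior-wall 'Other'.

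The gap between 100% and 83.3% is an illustration. It rests on invented counts, on no other extra-PV lesions being present, and on counting by lesion. The true size depends on how many lesions fall under 'Other' and how durable they are, which the documents do not give.

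**What to change.** 1. In the Secondary Feasibility part of SAP 2.5, add durability variables for the posterior wall and for other extra-PV sites from the 'Other 1' and 'Other 2' fields. Filter on the specification text: the index code shows that 'Other' can hold a pulmonary vein (LCPV is counted there as a PVI application), and veins must stay out of this endpoint. Use one harmonised list of posterior-wall terms for index and remap, since the two lists now differ.
2. Set each denominator to subjects ablated at that site at index and assessed there at remap. Replace the unconditional ELSE 'No' in the LAPW rule, so that subjects without the lesion are not counted as failures.
3. Replace the single Table 13 row with one row per lesion set: CTI, mitral isthmus, roof line, posterior line, posterior wall, other. If a pooled row is kept, state whether it counts lesions or subjects and by what rule.
4. Apply the interval rule of SAP 2.1.4 to each row.

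The cost is a few lines of derivation code and some table rows. The SAP already uses all the fields concerned, so no new data collection is needed.
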